Determine the effectiveness of the intervention compared with the standard-of-care in achieving the following:

1) PrEP-related outcomes following jail release (PrEP continuum of care):

- a) establish a primary care provider, who can prescribe PrEP,
- b) obtain screening for PrEP,
- c) begin PrEP,
- d) adhere to PrEP, and
- e) remain on PrEP for at least 3 months.

2) Infection and prevention screening tests in the community:

- a) HIV every 3 months,
- b) bacterial STIs every 6 months; and
- c) HCV at least once.

3) Obtaining and remaining engaged in treatment for substance use disorders (SUDs) in the community, according to each participant's recommended American Society of Addiction Medicine level of care.

Participant-related Study Methods

Overview

A total of 266 HIV-negative or HIV status unknown men who have sex with men (MSM) and transgender women (TGW) will be enrolled in this randomized controlled trial prior to being released from Men's Central Jail. Participants will be recruited from a unit of the jail that is designated as protective custody for self-identified gay and bisexual men and for transgender women. Participants will be randomized into either the standard-of-care condition or the intervention condition that involves an innovative new GPS-based mobile app and incentives for utilization of prevention-related services, in addition to the support of a Peer Mentor (app+incentives+PM). Each condition will include up to 150 participants. The standard-of-care condition will consist of the substance-abuse focused transitional case management and referral services provided by the LA Center for Alcohol and Drug Abuse's **Substance Treatment And Re-entry Transition program (Project START Program)**

1. Recruitment and screening

Study eligibility will be based on the following criteria:

- i. *Inclusion* 1) housed in K6G unit, 2) ages 18-44 years, 3) screens positive for SUDs via Project START, 4) reports condomless sexual intercourse with a male or male-to-female transgender woman in the six months prior to jail entry, 5) is likely to be remain custody for at least four more days, but less than 45 days based on scheduled court dates, current sentence, etc., 6) has not received an HIV diagnosis (based on self-report), and 7) plans to reside in Los Angeles County following jail release.

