Over the course of the study, intervention participants may receive up to \$500 total in gift card incentives for completing Passport activities. Most of these activities will take place over six months and are each valued at just \$5-15. These include medically related visits (HIV/STI/HCV screening, PrEP evaluation), substance abuse treatment appointments, in-person meetings with their study Peer Mentor or START program Case Manager, and non-medically related items on their Passports (e.g., support group meetings for gay and bisexual men or TG women or trainings at an employment service center). A full schedule of activities and the amount of accompanying incentives is provided below:

Passport Activity	Maximum	Amount
Link to a PCP who will prescribe PrEP	1	\$ 15
PrEP screening/evaluation	1	\$ 15
Begin PrEP	1	\$ 15
HCV test	1	\$ 15
STI tests	2	\$ 15
HIV tests	4	\$ 15
Substance abuse treatment services (including AA/NA meetings) or case managers	8-14	\$ 10
Meetings with PMs	14	\$ 5-15
Other	6-10	\$ 15

The Passport's incentive structure is designed to provide more compensation for those study components that are directly related to HIV/STD biomedical intervention or prevention, however, the largest portion is for SUD services that are likely to be recommended to occur much more frequently. Frequency for HIV (every 3 months)/STI (every 6 months)/HCV (at least once) screening is based on CDC recommendations for MSM at increased risk for HIV. For the SUD-related services, participants will only be compensated for the number of visits recommended per their American Society of Addiction Medicine (ASAM) level of care. In addition, the incentives are intended to encourage initial linkage visits to other needed services and then capped in order to avoid a situation in which participants repeatedly complete incentivized activities after they are no longer beneficial. Once participants take part in a particular service, resolve barriers to service access with a Peer Mentor, and identify providers they like, it is hoped that they will continue to engage with those services as, needed, regardless of the opportunity for an incentive.

c) Mobile Application

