## MEPS Outcomes and Statistical Data Analysis

### *Outcomes.*

Outcomes are indicators of achieving various milestones. Specific Aim 1 outcomes are measures of PrEP uptake: (a) primary care provider who can prescribe PrEP, (b) screening/evaluation for PrEP, (c) begin PrEP, (d) adhere to PrEP, (e) remain on PrEP for at least 3 months. Specific Aim 2 outcomes are whether study participants have sufficient preventive screening, (a) HIV screening every 3 months, (b) STI screening every 6 months, and (c) at least one HCV test. Specific Aim 3's outcome is that each participant be enrolled in appropriate SUDs treatment: (a) received any SUD treatment post-release; (b) attended some SUD treatment services appropriate to ASAM level; (c) met at least 70% of recommended treatment activities/frequencies for ASAM level of care. Outcomes of the secondary aims are (i) obtaining appropriate follow-up care for those who test positive for HIV, STI and HCV; (ii) lack of recidivism; and (iii) service utilization patterns. For all outcomes except the last, our primary hypothesis is that the control group will do worse, and our secondary hypothesis is that App+Incentives+PM arm will be more effective than the App+Incentives.

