### *Modeling Outcomes.*

Each outcome will be analyzed in longitudinal intention to treat using analyses of all available data from Baseline and 3-, 6-, and 12-month follow-up interviews, mobile app, and abstracted record data on utilization, as appropriate. For PrEP cascade outcomes from aim 1, the model is a logistic generalized linear mixed model (GLMM) with a random intercept for participants and a binary 0-1 outcome with 1 indicating success (screening for PrEP say) and 0 indicating a lack of success (not screening for PrEP). We generally do not expect participants to have any PrEP-related positive outcomes at baseline, and we anticipate using only follow-up data at 3, 6 and 12 months in the analysis of specific Aim 1 outcomes. The fixed effects will be a mean for every date (3, 6, 12 months) for each intervention group, for a total of 9 parameters. The first hypothesis is a test for each outcome of differences at 6 months; secondary tests are for differences at 3 months and at 12 months. If the three groups are different at a given time point, we will do pairwise comparisons among the treatments, particularly between the two intervention arms with and without PMs. Specific Aim 3 is similar, though there may be some participants with appropriate SUDs treatment prior to baseline, thus we will include the baseline observation as part of the outcome. At baseline, groups have not been affected by interventions, thus all groups will be the same, so there is one additional parameter for the baseline mean. Otherwise, the analysis is similar to Aim 1 outcome analyses.

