For specific Aim 2, the question in analyzing outcomes is whether the intensity (mean count) of health care visits per unit time is the same among the three groups. Thus, the analysis is a Poisson GLMM with log link and an offset equal to the log of the time covered by each observation, which models rates of visits per unit time. The advantage of this over binary logit GLMM modeling of 1=yes=had at least one visit in the past three months versus 0=no=no visits past three months, is that the binary model penalizes or rewards participants inappropriately for going a few days longer or shorter than 90 days in between visits. The parameter structure and statistical hypothesis testing is the same as for aim 1, though we estimate rate ratios instead of odds ratios. We will estimate the difference between the desired rate of visits (one per 3 months or per 6 months or per year) and the actual observed rate in each intervention arm.

Initial data analysis includes checking for out-of-range data and data cleaning. We will plot average outcomes and error bars as plus or minus two standard errors of the mean as a function of visit, broken out by intervention arm. These are called empirical summary plots. Weiss (2005) describes our general approach to modeling longitudinal data as will be generated by this study. A GLMM random intercept model can be fit in the SAS software Proc Mixed (Cary, NC 2017); if there are problems fitting the data in Proc Mixed, we will move to Bayesian software such as JAGS in R.

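### Outcome 2c (at least one HCV test) is a once-only milestone but is analysed as a Poisson visit rate over an unstated window, so the 6-month primary test may not compare the share who met it

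*SAP*

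**What the plan says.** The SAP (Outcomes) describes its outcomes as indicators of milestones and gives the third Aim 2 outcome as "c) at least one HCV test". The protocol's specific aims agree: "HCV at least once". Its Incentives section separates the two recurring targets from the single one: "Frequency for HIV (every 3 months)/STI (every 6 months)/HCV (at least once) screening is based on CDC recommendations". The incentive table there pays for at most one HCV test, against two STI and four HIV tests.

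SAP, Modeling Outcomes, sets one analysis for the whole of Aim 2: "the analysis is a Poisson GLMM with log link and an offset equal to the log of the time covered by each observation". Effects are reported as rate ratios. The stated reason for preferring this to a yes/no model is that "the binary model penalizes or rewards participants inappropriately for going a few days longer or shorter than 90 days in between visits". Observed rates are also to be compared with "the desired rate of visits (one per 3 months or per 6 months or per year", in the SAP's words. HCV is not mentioned in that section.

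For Aim 1 the same section uses "a binary 0-1 outcome with 1 indicating success", and it treats Aim 3 similarly. Aim 3 includes the milestone "received any SUD treatment post-release". The 6-month comparison is the first hypothesis for each outcome, and 3 and 12 months are secondary. Under Multiple Comparisons, 2c is one of 11 primary outcomes, and the global null is rejected when three or more reach p = 0.05.

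**The concern.** A milestone that needs to be met only once is naturally summarised by the share who have met it by a given date. The planned model compares a mean count per unit time instead, and the reason given for that choice concerns the spacing of repeat visits. A once-only target has no such spacing.

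What the 6-month rate measures depends on the time covered by the 6-month observation. Take a participant tested once, in month 2. That person has fully met 2c. If each observation runs from the previous interview, the person's rates are 1/0.25 = 4 per year at 3 months, 0 at 6 months and 0 at 12 months, and the primary contrast records no test. An intervention that brings testing forward could then show little or no effect at the primary time point while succeeding on the outcome as defined.

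**Working it through.** **The plan's own figures.** Under Power Calculations the SAP powers all 11 outcomes as 6-month probabilities of success. Its lowest powers, .958 at 133 per arm and .86 (printed as 86) at 100 per arm, are for (0.025, 0.075, 0.15) on 2 df. A simulated Pearson test gives .942 and .848, and an arcsine approximation gives .947 and .866. This confirms that the power basis is a test on proportions. It says nothing particular to HCV, because 2a and 2b are powered in the same way.

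**Inputs for the illustration.** The documents give no HCV testing rates or timing, so these are assumptions:
- n = 100 per arm (the SAP's figure after 25% attrition), two arms as in the protocol.
- Shares tested by 6 months of .30 and .65, the outer pair of the SAP's example (0.3, 0.5, 0.65). The SAP does not assign that example to HCV.
- At most one test per person, and half of control testers tested by month 3, leaving .15 in months 3-6.
- A fraction s of intervention testers tested by month 3, leaving .65(1 - s) in months 3-6.
- Independent participants (ignoring assignment by recruitment week or month), one outcome, two-sided .05.

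**Formulas.**
- Poisson test of the log rate ratio: SE used = sqrt(1/(n p1) + 1/(n p2)). The true SE for 0/1 data is sqrt((1-p1)/(n p1) + (1-p2)/(n p2)). Power = 1 - Phi((1.96 x SE used - ln RR)/SE true).
- Binary test: the usual two-proportion z test, with pooled SE under the null and unpooled SE under the alternative.

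**Observation covers the time since the last interview.** For s = .5 the contrast is .15 v .325, ln RR = .773, SE used .312 and SE true .278. Power = 1 - Phi((.612 - .773)/.278) = .72. The other columns follow in the same way.

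| | s = .5 | s = .6 | s = .7 |
|---|---|---|---|
| Intervention share tested in months 3-6 | .325 | .26 | .195 |
| Rate ratio | 2.17 | 1.73 | 1.30 |
| Power, cumulative share .30 v .65 | >.99 | >.99 | >.99 |
| Power, binary on months 3-6 | .83 | .49 | .13 |
| Power, Poisson on months 3-6 | .72 | .385 | .095 |
| Intervention share tested in months 0-3 | .325 | .39 | .455 |
| Power, Poisson at 3 months (control .15) | .72 | .91 | .98 |

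Restricting the window takes power from above .99 to .83, .49 or .13 even with a binary model. The Poisson variance removes a further .11 (.83 - .72), about .10 (.49 - .385) or about .04 (.13 - .095).

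These are single-date tests standing in for the mixed model. In 30 simulated data sets with at most one test per person, the fitted random-intercept SD was at its lower bound every time, so the mixed model reduced to plain Poisson.

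**Observation is cumulative from release, one test per person.** The model assumes variance p where the truth is p(1 - p), so the test is conservative. At p = .30, type I error = 2(1 - Phi(1.96/sqrt(.70))) = .019. For .30 v .50, SE used is .231 and SE true .183. Power is .625, against .80 for the same log-ratio test with the correct variance. For .30 v .65 it is .98 against .995.

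**The case against.** The rate may be deliberate. Three desired rates are listed for three Aim 2 outcomes, in the same order, and one per year over a 12-month follow-up amounts to at least one test. That is a fair reading, but the SAP never ties the yearly rate to HCV, and one per year does not express at least one test in a primary comparison at 6 months.

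A reader might infer that the Poisson model itself destroys the test. The table does not support this: most of the loss appears with a binary model on the same window. Nor is the window gap confined to 2c. The SAP does not say whether the yes/no milestones of Aims 1 and 3 are cumulative or since the last interview, so the Aim 3 milestone shows that a binary analysis was thought suitable elsewhere, not that the window is settled there.

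A reader might also infer that rate and share could point in different directions, or that false positives are inflated. That would need substantial repeat HCV testing, differing between arms. The documents do not suggest it, and the incentive covers one HCV test only. With one test per person counted cumulatively, type I error falls rather than rises.

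Finally, an early effect would not be invisible, since the 3-month test would usually detect it in these examples. That stands, but the 3-month test is secondary.

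**Conclusion.** The mismatch is real. 2c is defined as a once-only milestone, analysed as a visit rate for a reason that does not reach it, and left without any planned comparison of the share tested. The larger part of the potential harm is the unstated observation window. The Poisson variance is the smaller part, and the only part if counts are cumulative with one test per person.

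The size cannot be fixed from the documents. The power figures rest on assumed shares and timing, and on reading each observation as the time since the last interview. It would be tempting to conclude that the trial's overall decision is at risk. That is not shown: 2c is one of 11 outcomes, three rejections are needed, and nothing here establishes that the count would change. The point does not extend to 2a and 2b, whose targets recur and for which a rate is defensible.

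**What to change.** Define 2c as any HCV test from release through 6 months (primary), and through 3 and 12 months (secondary). Count earlier tests as successes, and compare arms with a logistic model at each date. Use data sources available in both arms, such as the follow-up interviews, since only the intervention arm has the app. Keep the Poisson model for 2a and 2b, and for 2c as a supportive analysis. State the time each observation covers.

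Use multiple imputation for unknown 6-month status; the SAP now plans imputation only for baseline predictors. A shortcut that carries successes forward and drops unknown non-testers would bias the shares. With 25% missing the 6-month interview and half of testers early in each arm, a true .30 becomes (.15 + .15 x .75)/(.15 + .85 x .75) = .33, and a true .65 becomes (.325 + .325 x .75)/(.325 + .675 x .75) = .68.

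No new data are needed. The cost is that repeat HCV tests no longer count in the primary analysis, 2c gives up the random-intercept longitudinal structure, and the SAP needs a source rule and a missing-status rule for this outcome.

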Participants *assigned to the intervention arm* will view pictures and short introductions to each of the available PMs, and then select the PM with whom he or she anticipates the greatest level of comfort and support. They may also select a back-up Peer Mentor, if circumstances make a given Peer Mentor unavailable. Next, the selected Peer Mentor will receive a copy of the Participant's passport and his or her contact information from the Project Director or RA and discuss with them the participants' major issues and strengths. Then he will arrange to meet the participant following their release from custody.

Peer Mentors will meet with their participants approximately every one to two weeks, for the first 8 weeks to provide support and guidance and to work with them to address barriers in accessing services listed in their Passport. They will also accompany them to key appointments, assist them in addressing other issues, and encourage productive communication with providers. Furthermore, the PMs will engage participants in ongoing evaluation of progress toward their goals and in considering new goals and Passport modifications. PMs will be trained to utilize Motivational Interviewing techniques to help participants resolve ambivalence that might undermine adherence to their services plan (i.e., Passport). After the first 2 months, participants will be expected to check-in with their PMs and meet in-person with their PMs less frequently. See **Intervention Schedule and Sessions**.

During the final 2 months, the Peer Mentors will begin working with the participants to strategize for a successful transition from peer mentorship and incentives. This will include identifying other external motivators as well as internal motivators for engaging in prevention-related services and behaviors and, if appropriate, encouraging participants to actively identify and engage members of their social network as supports in ongoing maintenance of their health-related goals. Ensuring this smooth transition will be a key focus of the last month of engagement and emphasized at the final in-person meeting. All participants completing the final session and at least 9 of their scheduled sessions will receive printed certificates of completion.

b. Incentives

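### The SAP does not define the period behind the 6-month Aim 2 rate; read as the interval since the 3-month interview, the primary STI test uses a 3-month window for a 6-month target

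*SAP*

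**What the plan says.** The three Aim 2 outcomes are "a) HIV screening every 3 months, (b) STI screening every 6 months, and (c) at least one HCV test" (SAP, Outcomes). The protocol's specific aims give the same targets.

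Visit counts are to be modelled on the log scale by a Poisson mixed model that includes "an offset equal to the log of the time covered by each observation, which models rates of visits per unit time" (SAP, Modeling Outcomes). For the rest, "The parameter structure and statistical hypothesis testing is the same as for aim 1". The Aim 1 text therefore governs Aim 2:

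- Parameters: "The fixed effects will be a mean for every date (3, 6, 12 months) for each intervention group".
- Primary test: "The first hypothesis is a test for each outcome of differences at 6 months".
- Other dates: "secondary tests are for differences at 3 months and at 12 months".

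The SAP does not say whether the time covered by an observation runs from the previous interview, over a fixed look-back, or from release. It mentions a three-month look-back only when describing the binary model that it rejects.

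In the intervention arm, peer mentors meet participants "approximately every one to two weeks, for the first 8 weeks to provide support and guidance" (Protocol, section 8a). In-person meetings become less frequent after the first two months.

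**The concern.** A recurring-visit rate needs a stated window, and here the window decides what the primary test measures. If the 6-month row covers only the time since the 3-month interview, the primary STI parameter is the rate in months 3-6, half the length of the target interval. Someone tested at month 1 and again at month 7 keeps the six-month schedule but adds no visit to the primary comparison. Someone first tested at month 5 adds one. A single HCV test at month 2 fully meets the HCV target and also adds nothing.

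If MEPS brings testing forward, as its early contact schedule makes plausible, early testers are not yet due again in months 3-6. The primary contrast would then understate the effect over the six-month intervention. Aim 2 supplies three of the 11 outcomes in the rule that needs at least three significant results (SAP, Multiple Comparisons), so weak tests here also weaken the global 6-month test.

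**Working it through.** **1. The plan's own figures.** The SAP's lowest power is .958 at 133 per arm and 86 (per cent) at 100 per arm, for success probabilities (0.025, 0.075, 0.15). A simulated three-arm Pearson chi-square on 2 df (200,000 draws) gives 0.942 and 0.848, both within two points. The pairwise claims of 0.8 power also reproduce: the minimum is 0.795 for a difference of 0.17 at 133 per arm, and 0.812 for 0.20 at 100 per arm. None of these figures uses an Aim 2 count or a look-back, so they do not settle the question.

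**2. Which window?** If every row ran from release, a test in month 2 would be counted in the 3-, 6- and 12-month rows of one model. A random-intercept Poisson model treats rows as independent given the intercept, which nested counts violate. Non-overlapping intervals are the coherent reading, so the 6-month row covers roughly months 3-6. This is an inference. A participant who missed the 3-month interview could also have a 6-month row covering months 0-6, which would mix windows within one mean.

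**3. Zero counts among participants on schedule (months 3-6 window).**

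- STI, first test uniform over months 0-6, then every 6 months: P(zero) = P(first test in months 0-3) = 3/6 = 50%.
- STI, first test in months 0-3: the next falls in months 6-9, so P(zero) = 100%.
- The same people always score 1 over months 0-6.
- HIV every 3 months, first test by month 3: the second falls in months 3-6, so zero does not occur.

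**4. Power.** Assumptions:

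- 100 per arm (the SAP's figure after 25% attrition), comparing two arms.
- Expected STI tests per person by month 6 of m0 (control) and m1 (MEPS), borrowed from the lowest and another value of the SAP's example probability triples. The SAP does not tie these triples to STI testing.
- Control tests spread evenly; a share f of MEPS tests falls in months 0-3.
- Poisson counts, Wald test of the log rate ratio, two-sided 0.05, no overdispersion and no allowance for assignment by recruitment period.

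Months 0-6: RR = m1/m0, SE = √(1/(100·m1) + 1/(100·m0)).
Months 3-6: replace m1 by m1(1−f) and m0 by m0/2.
Power = Φ(d − 1.96) + Φ(−d − 1.96), with d = ln(RR)/SE.

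For 0.30 vs 0.65 over months 0-6: RR = 0.65/0.30 = 2.17, SE = √(1/65 + 1/30) = 0.221, d = 3.50, power 0.94.
Over months 3-6 with f = 50%: RR = 0.325/0.15 = 2.17, SE = √(1/32.5 + 1/15) = 0.312, d = 2.48, power 0.70.

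Cells show rate ratio, then power:

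| m0 vs m1 | Months 0-6 | Months 3-6, f = 50% | f = 2/3 | f = 75% | f = 85% |
|---|---|---|---|---|---|
| 0.30 vs 0.65 | 2.17, 0.94 | 2.17, 0.70 | 1.44, 0.20 | 1.08, 0.06 | 0.65, reversed |
| 0.20 vs 0.55 | 2.75, 0.97 | 2.75, 0.78 | 1.83, 0.34 | 1.38, 0.12 | 0.83, reversed |
| 0.20 vs 0.60 | 3.00, 0.99 | 3.00, 0.85 | 2.00, 0.43 | 1.50, 0.17 | 0.90, reversed |
| 0.20 vs 0.80 | 4.00, >0.99 | 4.00, 0.98 | 2.67, 0.75 | 2.00, 0.43 | 1.20, 0.07 |

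The months 3-6 ratio falls below 1 once f exceeds 1 − m0/(2·m1): 77%, 82%, 83% and 88% for the four rows.

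**5. How to pool.** Averaging the 3- and 6-month log rate ratios does not give total visits over total time. For 0.30 vs 0.65 with f = 75%, the interval ratios are 0.4875/0.15 = 3.25 and 0.1625/0.15 = 1.08. Their geometric mean is √(3.25 × 1.083) = 1.88, while the ratio over months 0-6 is 2.17.

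**The case against.** The strongest reply is that the window is inferred. Under a since-release reading of the 6-month row nothing is lost, and the survey instrument, which is not among these documents, may settle the look-back. This stands: a reader might conclude that the SAP fixes the primary test to months 3-6, but it does not say so. The omission still needs repair, because the since-release reading fits poorly with a repeated-measures model.

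A reader might also infer that the first three months are discarded. They are not. They stay in the model, have their own arm means, and get a secondary 3-month test to which the multiplicity procedure is applied separately. The issue is which contrast is primary.

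A zero for one person is not an error in a rate model. With evenly spread testing, people on schedule average 0.5 STI tests per three months, which is the target rate. Bias between arms needs timing to differ by arm. The taper in peer contact makes that plausible. Against it, mentor, app and incentives run for six months, and the incentive schedule pays for up to two STI tests and four HIV tests (Protocol, section 8b), which may encourage later testing. The documents do not show which prevails. Even without a timing difference, the narrower window costs power (0.94 to 0.70 in the first row of the table).

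For HIV, a months 3-6 contrast is a defensible measure of sustained testing, since a test is due in that window.

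**Conclusion.** The point holds as an undefined interval with a material consequence under its natural reading. On that reading the primary STI test covers half the target interval, and early success on the STI or HCV target can score zero. HIV is affected only in that early tests do not count in the primary contrast.

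The size depends on assumed rates and timing. For 0.30 vs 0.65 tests per person and 100 per arm, the window alone takes power from 0.94 to 0.70 with the ratio unbiased at 2.17. With two thirds of MEPS tests in months 0-3 the ratio is 1.44 and power 0.20; with three quarters, 1.08 and 0.06. The other assumed rates lose less but follow the same pattern. Because overdispersion and clustering are ignored, the comparison between windows is more reliable than the power levels themselves.

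The documents do not support a claim that the test will point the wrong way. Reversal needs more than about 77% to 88% of MEPS tests in months 0-3 while control testing is even. Attenuation and lost power are the realistic risks.

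**What to change.** In the SAP, Modeling Outcomes:

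1. State that each Aim 2 row covers the non-overlapping interval since the last completed interview, or since release if there is none.
2. Make the primary 6-month contrast for STI screening, and for consistency HIV screening, the rate ratio from release to month 6. Compute it as total visits over total time, from collapsed 0-6 month records or a nonlinear contrast of the fitted rates, not as an average of log rate ratios.
3. Analyse HCV as at least one test by month 6.
4. Compute the desired-minus-observed STI rate over the same 0-6 month window.
5. Keep the months 3-6 rate as a secondary analysis.

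No new data are needed. The cost is slightly more analysis work than a single linear contrast, and participants with only one of the two interviews contribute only the time that it covers.
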